2.2.4 Summary of pharmaceutical development

Multi-dose Lagricel® Ofteno has been developed by Laboratorios Sophia, S.A. de C.V. It has the physicochemical characterization and the protocol of accelerated and long-term stability. The formulation is identical to that of Single-dose Lagricel® Ofteno with a Multi-dose presentation.

2.3. Research Background

2.3.1. Research question

There is no prior information on the efficacy of Multi-dose Lagricel® Ofteno in clinical studies. However, the efficacy and tolerability of Single-dose Lagricel® Ofteno has previously been evaluated in two single-center clinical studies. [32, 34, 33, 34].

In the two clinical studies of Single-dose Lagricel® Ofteno, TFRT, comfort, blurred vision, and the incidence of AEs were evaluated as outcome variables. Lagricel® Ofteno single-dose was well tolerated and the final results were statistically significant when compared with baseline values.

2.4. Risk-Benefit Evaluation

2.4.1. Potential known risks

Eye lubricants are safe formulations. SH has a known safety profile. The diagnostic tests considered in the study design are also considered safe.

It is only anticipated with the use of ophthalmic applications: burning, foreign body sensation and blurred vision. These are of mild intensity and transient, with a post-instillation duration of no more than one minute.

2.4.2. Known potential benefits

As subjects with a diagnosis of mild to moderate dry eye, they are expected to present improvement in ocular comfort in at least 1 of the dosages used during this study.

The benefits of the study will be to document the efficacy and establish the ideal dosage of Multi-dose

Lagricel® Ofteno.

2.5. Statement of the problem

Dry eye is a common disease, whose estimated prevalence varies widely depending on its classification. Although the pathogenesis of dry eye is multiple, the different treatment phases have as a common denominator the use of ocular lubricants.

There is a wide variety of topical lubricants; however, there is no evidence that one is better than another.

Ocular lubricants have not been shown to be sufficient to completely resolve the alteration of the ocular surface and inflammation observed in patients with dry eye, they have been shown to be effective in providing protection to the ocular surface and reducing symptoms and clinical findings.

Multi-dose Lagricel® Ofteno obtains from SH its viscoelastic, hypoosmolar and water retention properties, to function as an effective lubricant that protects the ocular surface and reconstitutes the tear film, without the association to a preservative.

2.5.1. Justification

Dry eye is defined as a multifactorial disease of the ocular surface. The tear film plays an essential role in lubricating and protecting the ocular surface, as well as optimal visual performance.

Patients with dry eye, regardless of their etiology and degree of severity, will have to use eye lubricants to reduce symptoms and improve their quality of life.

Ocular lubricants are the first line of treatment for eye symptoms related to dry eye in subjects who refer to them healthy, with a prevalence of 5 to 35% in people over 50 years of age. [35]

If we add patients with occasional symptoms or who depend on a work or occupational situation and who will use it for intermittent periods throughout their lives, the spectrum of the population that will have access to these drugs is very extensive.

It is estimated that 50% of patients diagnosed with dry eye without comorbidities will use more than 2 types of ophthalmic solutions in 5 years of treatment.

This is why preservative-free lubricants have gained importance, to reduce the deleterious effect of the accumulated dose of preservatives.

One of the disadvantages of preservative-free ophthalmic products is the single-dose presentation, which

makes the treatment more expensive for various reasons, including product shrinkage. With the development of new technologies, it has been possible to create a new generation of preservative-free products in multi-dose presentation.

Multi-dose Lagricel® Ofteno is a preservative-free lubricant in multi-dose presentation of which it is necessary to document its efficacy and determine its ideal dosage.

3. Objectives and hypotheses

3.1 Main objective

- To assess the efficacy of 3 dosages of Multi-dose Lagricel® Ofteno in patients with mild to moderate dry eye by improving OSDI score.

3.2 Specific objective

- To assess the safety of 3 doses of Multi-dose Lagricel® Ofteno in patients with mild to moderate dry eye by means of the incidence of unexpected AEs related to the investigational product.

3.3 Secondary objectives

- To determine the efficacy of the multi-dose formulation of Lagricel® Ofteno by changes in the TFRT in twice-daily (BID), four-times-daily (QID), and six-times-daily (6x/D) dosages.
- To determine the efficacy of the formulation of Multi-dose Lagricel® Ofteno by changing corneal and conjunctival stains with lissamine green in the BID, QID and 6x/D dosages.
- To determine the efficacy of the multi-dose formulation of Lagricel® Ofteno by changing corneal and conjunctival stains with fluorescein in the BID, QID and 6x/D dosages.
- To determine the efficacy of the multi-dose formulation of Lagricel® Ofteno by changes in conjunctival hyperemia in the BID, QID and 6x/D dosages.
- To determine the efficacy of the multi-dose formulation of Lagricel® Ofteno by the incidence of chemosis at the BID, QID and 6x/D dosages.
- To determine the safety of the multi-dose formulation of Lagricel® Ofteno by changes in BCVA at BID, QID, and 6x/D dosages.
- To assess the safety of the multi-dose formulation of Lagricel® Ofteno by changes in IOP at BID, QID, and 6x/D dosages.

3.4 Hypotheses

H₀: Multi-dose Lagricel® Ofteno decreases the OSDI test score by 20% or more at the end of the study in at least 1 of the proposed dosages.

H₁: Multi-dose Lagricel® Ofteno does not decrease the OSDI test score by 20% at the end of the study in at least 1 of the proposed dosages.

4. Study design

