5.1 Synopsis

Title of the study:
 
Phase II clinical study to evaluate the efficacy of the Multi-dose Lagricel® Ofteno ophthalmic solution in 3 different dosages for the management of mild to moderate dry eye
	

Study Number:
 
SOPH037-1219/II
	
Date of creation:
 
Dec 4-19

Protocol version:
 
2.0
	
Release Date:
 
February 20, 2020

Therapeutic indication:
 
Eye lubricant
	
Use:
 
Dry eye

Estimated duration of the study (from the first patient's first visit to the preparation of the final report): 7 months
	
Clinical Development Phase: II

Objectives:
 
Main objective:
 
 To assess the efficacy of 3 dosages of Multi-dose Lagricel® Ofteno in patients with mild to moderate dry eye by improving OSDI score. 
Specific objective:
 
 To assess the safety of 3 doses of Multi-dose Lagricel® Ofteno in patients with mild to moderate dry eye by means of the incidence of unexpected adverse events (AEs) related to the investigational product. 	

Hypothesis:
 
H₀: Multi-dose Lagricel® Ofteno decreases the OSDI test score (Ocular Surface Disease Index) by 20% or more at the end of the study in at least 1 of the proposed dosages.
 $H_0: P_A - P_B \leq \delta$ 
H₁: Multi-dose Lagricel® Ofteno does not decrease the OSDI test score by 20% at the end of the study in at least 1 of the proposed dosages.
 $H_1: P_A - P_B > \delta$	

Study Design:
 
Phase II, multicenter, comparative, controlled, parallel-group, open-label, randomized clinical trial.

Number of subjects (planned and analyzed):
 
n = 141 evaluable patients.
 
47 evaluable patients per group (3 groups in total) (both eyes [OU]).

Diagnosis and main inclusion criteria:
 
- Patients with mild to moderate dry eye.

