Safety primary outcome variable:

- Incidence of AEs (ET: days 15 and 31).

[figure not shown]
Safety Secondary Outcome Variable:

- Changes in the BCVA (ET: day 15 and 31).
- Changes in intraocular pressure (IOP) (ET: day 15 and 31).

Statistical methodology

The Kolmogorov-Smirnov and Shapiro Wilk tests will be performed, as appropriate, to know if the distribution presents normality in the results obtained in each study group. The data will be expressed with measures of central tendency: mean and standard deviation for the quantitative variables. Qualitative variables will be presented in frequencies and percentages. The statistical analysis will be performed by means of the Analysis of Variance Test (ANOVA) for the quantitative variables for the difference between the groups. The difference between the qualitative variables will be analyzed by means of X² (Chi-square) or Fisher's exact. A 95% CI will be considered for the non-inferiority criteria based on the objectives of the study, an alpha (α) will be considered significant ≤ 0.05

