5.1 Eligibility criteria

5.1.1 Inclusion criteria

- Be of legal age.
- Have the ability to voluntarily give their signed informed consent.
- Be able and willing to comply with scheduled visits, treatment plan, and other study procedures.
- Be willing to modify lifestyle activities.
- Women of childbearing potential must ensure the continuation (initiated ≥ 30 days prior to signing the ICF) of the use of a hormonal contraceptive method or IUD during the study period.
- Have a diagnosis of mild to moderate dry eye, defined by:
 - OSDI from 13 to 32 points
 - + 1 of the following:
 - Corneal staining with more than 5 sites.
 - Conjunctival staining with more than 9 sites.
 - TFRT < 10 seconds.

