7.4 Outcome variables

7.4.1 Primary outcome of efficacy

- OSDI test score (ET: day 31).

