10.1.2 Data interpretation

The Kolmogorov-Smirnov and Shapiro Wilk tests will be performed, as appropriate, to determine if the distribution is normal in the results obtained in each study group [59].

The results of the continuous quantitative variables will be presented in measures of central tendency: mean, standard deviation and/or range.

- Intragroup analysis: Differences within groups will be analyzed using the one-way ANOVA or the Student's t-test when applicable.
- Inter-group analysis: For equal variances, Tukey's post-hoc test will be used, otherwise Dunnett's statistic will be used. Student's t-test will be used when applicable.

The level of difference to consider significance will be an alpha (α) of 0.05 or less. A 95% confidence interval (95% CI) will be considered for non-inferiority criteria [60].

The result of the nominal and ordinal qualitative variables will be presented in frequencies, proportions and percentages.

The statistical analysis to identify significant differences in the qualitative variables will be carried out by creating 2x2 contingency tables and will be carried out as follows:

- Intra-group difference: McNemar test. This is applied to 2x2 contingency tables with a dichotomous feature, with pairs of paired subjects, to determine if the marginal frequencies of row and column are equal (marginal homogeneity).
- Difference between groups: Pearson's Chi-square test (X^2) or Fisher's exact test at expected values less than 5.

The level of difference to consider significance will be an alpha (α) of 0.05 or less.

For the reporting of AEs, all eyes of those participants who were randomly assigned to an intervention group after the baseline visit will be considered. The results will be expressed in number of subjects.

The final report of the results will be shown in tables or graphs, as appropriate.

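### The worded hypotheses make efficacy the null, and no planned test or success rule addresses the 20% OSDI criterion

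*Combined protocol and SAP*

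**What the plan says.** - **Hypotheses (section 3.4, repeated in the Synopsis).** H0 is that the product "decreases the OSDI test score by 20% or more at the end of the study in at least 1 of the proposed dosages". H1 is that it "does not decrease the OSDI test score by 20% at the end of the study in at least 1 of the proposed dosages".
- **Symbols (Synopsis and section 10.2.2).** H0: P_A - P_B ≤ δ; H1: P_A - P_B > δ. Section 10.2.2 calls δ a non-inferiority margin of 10%.
- **Main objective (section 3.1).** Efficacy of three dosages "by improving OSDI score", with no threshold.
- **Primary outcome (section 7.4.1).** The OSDI score at day 31. Table 3 schedules it at the basal and final visits and lists ANOVA and, when applicable, Student's t.
- **Analysis.** The Synopsis plans an "Analysis of Variance Test (ANOVA) for the quantitative variables for the difference between the groups". Section 10.1.2 adds: "Differences within groups will be analyzed using the one-way ANOVA or the" Student's t test, then Tukey or Dunnett between groups, alpha 0.05, and a 95% CI for non-inferiority criteria that it does not define.
- **Sample size (section 10.2.2).** A 20% OSDI decrease relative to the initial mean is assumed. A two-proportion formula with 80% power and alpha 0.05 gives 39 per group, raised to 47.

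**The concern.** A significance test can reject a null hypothesis but cannot establish it. With efficacy as H0, the only outcome favourable to the product is a failure to reject, and noisy or sparse data make that more likely. The burden of proof is reversed.

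The second gap is that the 20% criterion is never connected to an analysis. The listed tests ask whether dosages differ or whether OSDI changed. No rule says what result would show that at least one dosage met 20%, or how the error rate is controlled over three attempts. In an open-label study, that leaves the deciding test and success criterion to be chosen after the results are known.

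**Working it through.** **1. The wording.** H0 asserts a fall of 20% or more in at least one dosage and H1 denies it. Read literally the two overlap: if one dosage reaches 20% and another does not, both can be true. Reading H1 as meaning none of the dosages (perhaps a translation effect) removes the overlap but leaves efficacy in the null.

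**2. The symbols.** They do not translate the wording. P_A, P_B, the comparator and the sign of δ are not given, all three arms receive the same product, and no responder proportion is an outcome. The plan's own figure shows the gap. The formula is n = [P_A(1-P_A) + P_B(1-P_B)] x [(z(1-α) + z(power)) / (P_A - P_B - δ)]², with z sum 1.645 + 0.842 = 2.486.
- P_A = P_B = 0.20, δ = ±0.10: 0.32 x (2.486/0.10)² = 197.8, so 198.
- 0.20 against 0.10, δ = -0.10: 0.25 x (2.486/0.20)² = 38.6, so 39. This requires 10% to be one of the proportions as well as the margin, which the text does not say.
- 39 x 1.2 = 46.8, so 47; 3 x 47 = 141.

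The 39 therefore cannot be traced to stated inputs. Either way it is a two-proportion calculation, not a test of a mean OSDI reduction.

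**3. What the planned tests answer.**
- *ANOVA, Tukey or Dunnett between dosages.* Simulated with 47 per arm and an assumed SD of 35 points, ANOVA rejects 4.9% of the time when every arm falls by 0% and 5.0% when every arm falls by 30%. It carries no information on 20%.
- *Student's t on change from baseline, with the usual null of zero (section 10.1.2 names no null value).* At a true 10% reduction, 47 per arm, two-sided 0.05 and assumed SDs of 25, 35 or 50 points, it is significant 77, 48 or 27% of the time although 20% is not met.
- *Any of three.* Three separate tests at 0.05 give a family-wise error of up to 1 - 0.95³ = 14.3% if independent. No rule covers this.

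**4. Power of a test that does address 20%.** For each subject let D = 0.8 x OSDI(BV) - OSDI(FV). If the group mean falls by r%, the mean of D is (r - 20)% of the baseline mean. A dosage passes if the one-sided lower bound for the mean of D exceeds 0.

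Assumptions: SD of D at 20, 30, 40 or 50% of the baseline mean (the documents give none), r = 30% in every arm, independent arms, one-sided 0.05/3 = 0.0167. Noncentrality is 10√n/SD. Critical t is 2.208 at n = 39 and 2.194 at n = 47. At least one of three = 1 - (1 - p)³.

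| SD | p per arm, n=39 | At least one, n=39 | p per arm, n=47 | At least one, n=47 |
|---|---|---|---|---|
| 20 | 0.816 | 0.994 | 0.888 | 0.999 |
| 30 | 0.457 | 0.840 | 0.540 | 0.903 |
| 40 | 0.270 | 0.611 | 0.324 | 0.691 |
| 50 | 0.180 | 0.448 | 0.215 | 0.516 |

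The n per arm for 80% is 17, 36, 61 or 94. If one dosage falls by 30% and the other two by 20%, power at n = 39 is 1 - (1 - p)(1 - 0.0167)², or about 82, 47, 29 or 21%. At r = 20% in all arms, the plan's own planning effect, it is 1 - (1 - 0.0167)³ = 4.9%, whatever the SD or n.

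**The case against.** The best defence is that the intent is clear and the material for a proper test is present. The 20% threshold, its reference to the initial mean, the end of study and the any-dosage claim are all prespecified. OSDI is collected at both visits, an intragroup t test is planned, and the main objective carries no threshold. That stands. It makes the plan underspecified rather than the trial incapable, but it supplies neither a test against 20% nor a success rule.

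Four stronger readings are tempting and are not supported:
- *The trial cannot show efficacy.* It can still estimate OSDI change and compare dosages, and the 20% criterion is testable with the planned data. The defect is in the plan as written.
- *The inversion gives a calculable chance of passing an ineffective product.* Any such figure needs a test that tries to reject the worded H0 in all three arms. The documents plan none, so the inversion has no numerical size of its own.
- *The symbols contradict the wording in direction.* With P_A, P_B and the sign of δ undefined, their direction cannot be established.
- *The trial has only about 5% power.* That holds only if a dosage must be shown to exceed 20%. If instead 20% were the target and 10% a margin on the same scale, a bound above 10% at a true 20% is again a 10-point distance. With the same assumed SDs, power at 39 per arm would be the same 99, 84, 61 or 45%. The margin's scale is undefined, so the documents settle neither rule.

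**Conclusion.** The point holds and should be corrected before analysis. Efficacy is written as the null in both places where the hypotheses are worded, and the symbolic pair does not rescue it. No planned analysis is specified against 20%, and no success rule or error rate covers at least one of three dosages. A significant or non-significant ANOVA, or a t test of change from baseline, therefore does not answer the stated hypothesis.

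This rests on the text and needs no numerical assumption. The power table is illustrative: it depends on assumed SDs, a true 30% reduction, independent arms and the bound-above-20% rule. Under that rule one result needs no SD: because the planning effect equals the threshold, power at that effect cannot exceed the chosen alpha. The stated 80% should not be attached to the 20% criterion.

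**What to change.** 1. In section 3.4, the Synopsis and section 10.2.2, state one pair. H0: the OSDI reduction from baseline to day 31 is 20% or less in every dosage. H1: it exceeds 20% in at least one dosage.
2. Name the test: Student's t within each dosage on 0.8 x OSDI(BV) - OSDI(FV), with success if the one-sided lower confidence bound exceeds 0. This matches the group-mean definition in section 10.2.2.
3. State a family-wise alpha over the three dosages, for example Holm at one-sided 0.05 (first step 0.0167). Level and method are the sponsor's choice.
4. Keep ANOVA and Tukey as a separate between-dosage comparison.
5. Delete the non-inferiority sentence in the Synopsis and section 10.1.2, or tie the 10% margin to a comparator, variable and sign.
6. Restate power for this test with a stated SD and an assumed true reduction above 20%.

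**Cost.** A protocol amendment through the committees and COFEPRIS (section 11.2). No new visits or measurements are needed, since OSDI is already taken at both visits, and the change itself requires no extra patients. The stated power may fall below 80%: under the assumptions above, an SD of 40 or 50 would need 61 or 94 per arm against the planned 47. Whether to accept the lower power or enlarge the trial is a separate decision.

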10.2.2 Justification of the sample size calculation

The sample size calculation was made based on the study by Pinto-Fraga et al. (2017), where they evaluated the safety and efficacy of an artificial tear of 0.2% hyaluronic acid (HA) versus SS (saline, 0.9% NaCl) in patients with mild dry eye (OSD) after one month of treatment. Subjects treated with HA had a decrease of -19.66% with respect to their initial mean value, while in subjects treated with SS there was a significant increase in the final OSDI score of 12.47%, $p < 0.05$ compared to the initial [61].

For the calculation, a decrease in the OSDI score of 20% was considered for the formulation proposed in this protocol (Multi-dose Lagricel® Ofteno) with respect to its initial mean value in subjects with mild to moderate DED.

The sample size was calculated using the equation for two proportions [62], considering a power of 80% (β), a significance level of 0.05 (α) and a non-inferiority margin (δ) of 10%, based on the following working hypotheses:

$$H_0: P_A - P_B \leq \delta$$

$$H_1: P_A - P_B > \delta$$

Where, δ is the margin of non-inferiority and the ratio between the sample size of the two groups is:

$$k = \frac{n_A}{n_B}$$

The calculation to estimate the sample size and power was done using an online tool and following the equations [63]:

$$n_A = kn_B, n_B = \left(\frac{P_A(1 - P_A)}{k} + P_B(1 - P_B) \right) \left(\frac{z_{1-\alpha} + z_{B-\beta}}{P_A - P_B - \delta} \right)^2$$
$$1 - \beta = \Phi(z - z_{1-\alpha}) + \phi(-z - z_{1-\alpha}), z = \frac{P_A - P_B - \delta}{\sqrt{\frac{P_A(1 - P_A)}{n_A} + \frac{P_B(1 - P_B)}{n_B}}}$$

Where:

- $(k = \frac{n_A}{n_B})$ is the allocation ratio,
- (Φ) is the standard normal distribution function,
- (α) is the Type I error,
- (β) is the Type II error, meaning that $(1 - \beta)$ is the power, and
- (δ) is the test margin.

According to the previous calculation, the result is 39 subjects, this calculation was increased by 20% considering possible losses (8 subjects). The total suggested sample size is 141 subjects (47 subjects per treatment dosage), who will contribute OU to the study.

11. Ethical considerations

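### The 80% power in 10.2.2 is not the power for the efficacy criterion in 3.4, because the criterion (an OSDI fall of at least 20%) equals the effect assumed in planning (20%) and no test against it is named

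*Combined protocol and SAP*

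**What the plan says.** - **Criterion.** Section 3.4, like the synopsis (numbered 5.1), frames efficacy as the product achieving a result that "decreases the OSDI test score by 20% or more at the end of the study in at least 1 of the proposed dosages". This statement is labelled H0. The alternative is that "Multi-dose Lagricel® Ofteno does not decrease the OSDI test score by 20% at the end of the study".
- **Planning effect.** Section 10.2.2 cites a trial of 0.2% hyaluronic acid: "Subjects treated with HA had a decrease of -19.66% with respect to their initial mean value". It then says: "For the calculation, a decrease in the OSDI score of 20% was considered for the formulation proposed in this protocol".
- **Power.** The calculation uses an equation for two proportions, "considering a power of 80% (β), a significance level of 0.05 (α) and a non-inferiority margin (δ) of 10" (the last figure is a percentage). PA and PB are not stated. The outcome is that "the result is 39 subjects, this calculation was increased by 20% considering possible losses (8 subjects"), which gives 47 per group and 141 in total. Section 10.1.4 ties the 141 to the primary objective.
- **Analysis.** Section 10.1.2 and Table 3 (7.4.5) name ANOVA and Student's t-test, with Tukey or Dunnett comparisons between groups. The synopsis and 10.1.2 also mention a 95% confidence interval for non-inferiority. Nothing tests a dosage against a 20% fall, and no rule says when the 20% counts as reached.

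**The concern.** The 20% does two jobs: it is the fall assumed for the product and the bar that the product must reach. When the true value lies on the bar, a larger sample does not raise the chance of showing that the bar is exceeded. So the 80% in 10.2.2 cannot describe the criterion in 3.4, although 10.1.4 presents the sample size as sufficient for the primary objective. A reader of the final report could not tell what chance the trial had of meeting its own criterion, or how often the criterion would be met by a product that falls short of 20%.

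**Working it through.** **1. The plan's own figure.** The formula with equal allocation is n = [PA(1−PA) + PB(1−PB)] × [(z(1−α) + z(power)) / (PA − PB − δ)]². At one-sided 5% and 80% power, z(1−α) + z(power) = 1.645 + 0.842 ≈ 2.486.

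- PA = 20%, PB = 19.66%, δ = +10%: 211. With δ = −10%: 184.
- PA = PB = 20%: 198.
- PA = 20%, PB = 12.47%, δ = −10%: 54.
- PA = 20%, PB = 10%, δ = −10%: 0.25 × (2.486/0.20)² = 38.6, so 39.

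The 39 can thus be reached with a PB of 10%, which the protocol does not state. It cannot be confirmed from the stated inputs. The step to 47 is 39 × 1.2 = 46.8. None of these calculations involves a single dosage compared with a 20% fall.

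**2. True fall equal to the bar (20% and 20%).** No SD is needed.

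- Formal test against 20%, one-sided 5%: 5% per dosage. For at least one of three independent arms, unadjusted: 1 − 0.95³ = 14.3%.
- Lower limit of a two-sided 95% interval: 2.5% per dosage; 1 − 0.975³ = 7.3% for at least one.
- Point estimate at or above 20%: 50% per dosage; 1 − 0.5³ = 87.5% for at least one. A simulation with baseline scores spread over 13 to 32 gave 49.7% to 50.3% per dosage at 39, 47 and 500 per arm.

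**3. Assumptions for the remaining steps.** The documents give no SD. Assume a baseline mean of 22.5 (the middle of the 13 to 32 entry range), an SD of change of 8, 10 or 12 points, and 39 per arm. The standard error of the percentage fall is SD/(√39 × 22.5) = 5.7, 7.1 or 8.5 percentage points.

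**4. Point-estimate rule when every dosage falls short.** At a true fall of 15% and SD 10, the bar is 5/7.12 = 0.70 standard errors away. Each dosage reaches it with probability about 24%, and at least one of three with 1 − 0.76³ ≈ 56%.

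**5. Within-group test against no change, true fall 20%.** Power is Φ(20/SE − 1.645) = 97%, 88% and 76% for SD 8, 10 and 12 (one-sided 5%). With 1.960 in place of 1.645 (two-sided 5%) it is 94%, 80% and 65%.

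**6. Bar lowered to 10% by the margin, true fall 20%.** Φ(10/SE − 1.645) = 54%, 41% and 32%. If instead the SD of the individual percentage change is 30 points, SE = 30/√39 = 4.80 and power is 67%. For SDs of 20, 40 and 50 points it is 93%, 47% and 35%.

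**7. True fall needed for 80% power against 20%, one-sided 5%.** This is 20 + 2.486 × SE.

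| Assumption | Per arm | True fall needed |
|---|---|---|
| SD of change 8, 10, 12 points | 39 | 34.2%, 37.7%, 41.2% |
| SD of change 8, 10, 12 points | 47 | 32.9%, 36.1%, 39.3% |
| SD of percentage change 20, 30, 40, 50 points | 39 | 28.0%, 31.9%, 35.9%, 39.9% |

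**The case against.** The strongest reply is that the test against 20% is not in the plan. The named within-group t-test has a null of no change, and at a true 20% fall its power is respectable (step 5). This stands. The alpha result is conditional on a test that someone would have to add. But a test of zero does not answer 3.4, and the 80% was not derived for it either.

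Second, the synopsis prints PA − PB and δ directly under the verbal hypotheses, and 10.2.2 sets δ at 10%. If that margin is taken off the 20%, bar and planned effect no longer coincide. This also stands as a possible reading, although the verbal hypothesis contains no margin and δ is defined for a difference of two proportions. Under the main assumptions power is then still only 32–54%. On the percentage-change scale it passes 80% only at the smallest SD tried, 20 points.

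Third, 20% may be meant as a minimum target, and 6.1.2.1 regards four times daily as the optimal dosage. All three dosages at exactly 20% is then a stylised case, and a dosage with a larger true fall would do better. That is fair, but 10.2.2 names no other effect to plan on.

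Fourth, H0 and H1 are reversed as written, so a test that retains H0 would nominally favour the product. That is a separate defect. It would not demonstrate efficacy, and exchanging the labels leaves the two 20% figures equal.

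A reader might go further and infer that the trial most likely cannot show efficacy if the product performs as planned. The documents do not support that. Success is worded as at least one of three dosages, and by point estimate this happens 87.5% of the time at a true 20%. The conclusion would hold only under a formal test without a margin, which is not specified.

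**Conclusion.** The point holds in this form: the stated 80% is not the power for the 20% criterion, and the plan leaves open how that criterion is judged. The trial's chance of success at the planned effect depends on the rule chosen. It is about 14% for at least one dosage by unadjusted one-sided tests against 20%, and 87.5% by point estimate. The point-estimate rule has no error control: about 56% when every dosage truly falls only 15%. The 14% and 87.5% need no SD; they assume only that all three dosages truly give 20%, with approximately normal estimates from independent arms. The other figures rest on the assumed baseline mean and SDs and should be read as ranges. What must be corrected is the power statement and the missing decision rule. Whether the bar should be lower than 20% is a judgement for the sponsor.

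**What to change.** - **10.1.2:** name the test and decision rule for the 20% criterion, for example a one-sided confidence bound for the percentage fall in each dosage, and say how multiplicity for at least one of three is handled.
- **10.2.2:** replace the 80% statement with the true fall at which the planned number gives 80% power against 20%, with the baseline mean and SD stated. The unadjusted figures in step 7 show the scale; a multiplicity adjustment would raise them.
- **Synopsis (5.1) and 3.4:** if the tested claim is meant to be any fall from baseline, or a bar below 20%, say so and restate the power for that claim.

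The cost is wording in these four places and a less favourable stated power. No patients are added.

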6.1 Administered product

1. Investigational product

- Generic name: Sodium hyaluronate.
- Distinctive name: Multi-doses Lagricel® Ofteno.
- Active ingredients: Sodium hyaluronate 0.4%.

- 
- Pharmaceutical form: Ophthalmic solution.
 - Presentation: Multi-dose dropper bottle.
 - Prepared by: Laboratorios Sophia, S.A. de C.V.
 - Solution Description: Transparent solution, free of visible particles.
 - Packaging description: White bottle with a capacity of 10 mL, made of low-density polyethylene.

2. Dose of the investigational medicinal product

Three different dosages will be used, each of the groups will use one of the following:

- One drop BID, OU, for 30 days (suggested time between applications is 12 hours).
- One drop QID, OU, for 30 days (minimum time between applications of 3 hours).
- One drop 6x/D, OU, for 30 days (minimum time between applications of 3 hours).

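### The at-least-one-of-three OSDI success rule has H0 and H1 reversed, no named test against 20%, and no control of alpha over the three dosages

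*Combined protocol and SAP*

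**What the plan says.** - **Success rule.** H0 in section 3.4 (and in the synopsis) says that the product lowers the OSDI score "by 20% or more at the end of the study in at least 1 of the proposed dosages". H1 says that it "does not decrease the OSDI test score by 20% at the end of the study in at least 1 of the proposed dosages".
- **Arms.** Section 6.1: "Three different dosages will be used, each of the groups will use one of the following". The study is randomized with parallel groups and has no untreated or placebo arm.
- **Alpha.** Section 10.1.2: "The level of difference to consider significance will be an alpha (α) of 0.05 or less". It gives neither sidedness nor a split over dosages.
- **Tests.** Within a group: "Differences within groups will be analyzed using the one-way ANOVA or the Student's t-test when applicable". Between groups: Tukey's post-hoc test, or Dunnett's statistic if variances are unequal. Table 3 lists ANOVA and Student's t for the OSDI. None of these is set against a 20% threshold.
- **Interval.** "A 95% confidence interval (95% CI) will be considered for non-inferiority criteria". The interval is tied to non-inferiority, not to the 20% criterion.
- **Sample size.** Section 10.2.2 uses a two-proportion non-inferiority formula, "considering a power of 80% (β), a significance level of 0.05 (α) and a non-inferiority margin (δ) of 10" per cent. The formula takes the one-sided normal quantile at 1 − alpha. The assumed effect is a 20% fall from the initial mean.

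**The concern.** The main objective is efficacy by improvement in OSDI score, and the hypothesis gives the product three independent chances to meet it. Three gaps combine.

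1. With success printed as H0, rejecting H0 would mean failure. Alpha then limits the risk of wrongly declaring failure and places no limit on wrongly declaring success.
2. Without a named test against 20%, an analyst could test each dosage at 0.05, test change from zero, or read off whether any observed mean fall reaches 20%. These procedures have very different error rates.
3. Whichever is used, nothing accounts for taking the best of three. Tukey and Dunnett answer whether dosages differ from one another, not whether a given dosage reaches 20%.

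At stake are the efficacy conclusion and the size of the effect reported for the selected dosage, since the best of three estimates tends to overstate. The protocol says the study is meant to document efficacy and establish the ideal dosage.

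**Working it through.** **The plan's own figure.** Section 10.2.2 gives 39 per group but no values for P_A and P_B. With one-sided alpha 0.05 and 80% power, 39 is recovered if P_A = 0.20, P_B = 0.10 and δ = −0.10. The 0.10 for P_B is my assumption.

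n = (0.20 × 0.80 + 0.10 × 0.90) × ((1.645 + 0.842) / 0.20)² = 38.64, so 39.

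Then 39 × 1.2 = 46.8, so 47 per group, and 3 × 47 = 141. The 80% power thus belongs to a one-sided, two-group comparison of proportions. It is not the power of any dosage's test against a 20% fall.

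**If each dosage were tested against 20% at 0.05.** The arms are independent, so P(at least one false success) = 1 − (1 − a)^k, where a is the favourable-direction error per dosage and k is the number of dosages exactly at the threshold.

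| Case | a | k | Result | Ratio to 0.05 |
|---|---|---|---|---|
| One-sided 0.05 | 0.05 | 3 | 1 − 0.95³ = 14.3% | 2.85 |
| One-sided 0.05 | 0.05 | 2 | 1 − 0.95² = 9.8% | 1.95 |
| Two-sided 0.05 | 0.025 | 3 | 1 − 0.975³ = 7.3% | 1.46 |
| One-sided 0.05/3 | 0.0167 | 3 | 1 − 0.9833³ = 4.9% | 0.98 |

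Simulation of three one-sample t-tests at one-sided 0.05 gave 14.1% with 39 per arm and 14.2% with 47.

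**If the best point estimate were read off.** Assume that every arm truly falls by 15% and that the SD of percent change is 30, 40 or 50 points. The documents give neither figure. Per arm, p = 1 − Φ(5 / (SD/√n)); for any arm, 1 − (1 − p)³.

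| n per arm | SD | p per arm | At least one of three |
|---|---|---|---|
| 39 | 30 | 0.149 | 38% |
| 39 | 40 | 0.218 | 52% |
| 39 | 50 | 0.266 | 60% |
| 47 | 30 | 0.127 | 33% |
| 47 | 40 | 0.196 | 48% |
| 47 | 50 | 0.247 | 57% |

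**Power of a corrected test against 20%.**
- If the true fall in every arm is the planned 20%, each test at one-sided 0.05/3 rejects with probability 1.7%, and at least one rejects with probability 4.9%. With two-sided 0.05/3 (favourable error 0.0083 per dosage) the latter is 1 − 0.9917³ = 2.5%.
- If the true fall is 25% in every arm, a one-sided t-test at 0.05/3 has non-centrality 5 / (SD/√n). For SDs of 30, 40 and 50, power per dosage at 39 per arm is 13.2%, 8.5% and 6.4%, so 35%, 23% and 18% for at least one. At 47 per arm the latter figures are 40%, 27% and 20%.

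**The case against.** A reader might infer that the plan judges each dosage at 0.05 and that its false-success rate is therefore nearly three times alpha. The documents do not support that. No per-dosage test against 20% is written, so 14.3% is the error rate of a procedure the plan does not contain. It also requires one-sided tests and all three dosages exactly at the threshold. Only the sample-size formula is one-sided; section 10.1.2 is silent, and two-sided tests give 7.3%. Any dosage truly below the threshold lowers these figures.

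The point-estimate figures also rest on assumptions. The only stated falls on hyaluronate are 20% and 19.66%, and no SD is given. Section 10.2.2 speaks of a fall relative to the initial mean, which need not equal a mean of individual percent changes. The figures illustrate the risk and do not predict the result.

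Two further points are fair. A Phase II dose-finding study may accept a looser error rate, and the five secondary efficacy outcomes also inform the conclusion. Neither removes the gap: a looser rate has to be stated, and the written hypothesis rests on OSDI alone. For comparisons between dosages, the Tukey or Dunnett provision does answer the multiplicity question.

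**Conclusion.** The point holds in this form: the at-least-one rule has inverted hypotheses, no defined test against 20%, and no control of the single 0.05 over three dosages. This is more than missing detail, because an analyst who follows the plan as written has no bound on false success. The size depends on which procedure is used:

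- about 7% (two-sided) to 14% (one-sided) if each dosage were tested at 0.05 with all three at the threshold;
- 33% to 60% if the best point estimate were read off, under an assumed true fall of 15%, SDs of 30 to 50 points and 39 to 47 per arm.

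The repair should be made before analysis, but it does not call for a change of design unless the sponsor wants adequate power to show a 20% reduction.

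**What to change.** 1. In the synopsis and section 3.4, state the null as no dosage reaching the 20% reduction and the alternative as at least one dosage reaching it. Reconcile this with the two-proportion non-inferiority hypotheses in the synopsis and section 10.2.2.
2. In section 10.1.2 and Table 3, name one per-dosage test, its sidedness and the exact measure (mean of individual percent changes, or percent change in the group mean).
3. Apply Holm, or alpha/3 per dosage (98.3% intervals if two-sided), so that the overall error is at most 0.05. Claim a 20% reduction only for a dosage whose adjusted test or interval supports it.
4. Restate the power. The 80% in section 10.2.2 does not apply to this claim; at the planned 20% fall the chance that any dosage succeeds is about 5%.

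If that is unacceptable, the alternative is to test change from baseline per dosage with the same adjustment, and to report the 20% criterion descriptively with its operating characteristics. With no untreated arm, that claim is change from baseline only.

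**Cost.** Steps 1 to 3 are changes of wording. Step 4 is a real cost: keeping a formal test against 20% at adequate power would need a larger assumed effect with a matching sample size, or a different threshold.
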